## 1. Abstract

Thrombectomy has significantly improved stroke outcomes. Nearly 80% of our clinic population now present with small strokes and low NIH Stroke Scale (NIHSS) scores. However, despite “good recoveries”, greater than 40% endorse significant problems with higher-level cognitive functions, mood disorders, and fatigue. The natural history and pathophysiology of these deficits are not as well described as motor or language deficits; but they are equally debilitating, preventing previously high-functioning active individuals from returning to their prior workplace and social environments. This can be particularly difficult for the elderly, resulting in early retirement and loss of independence. The pathophysiology underlying these deficits remains unclear. Impairments in executive function and processing speed occur independent of stroke size, location, or depression. Using magnetoencephalography (MEG), a tool able to evaluate neurophysiologic processes in real time akin to EEG with better spatial resolution, *we have found that cerebral activation patterns are slowed and more diffuse during task completion in stroke patients compared to controls*; and at rest there is **abnormal activity in the frontal lobes**, an area critical for executive function, processing speed, affect regulation, and decision making. Some patients improve over months; however, recovery is variable and by this time many have made critical life decisions. There is little data regarding effective treatment options. The ability to hasten improvement would significantly improve morbidity in a group with excellent recovery potential.

Mindfulness has been practiced since ancient times, but only recently gained popularity as an effective treatment for anxiety and depression both in normal individuals and those with chronic disease states. Mindfulness Based Stress Reduction (MBSR) has also been evaluated in a small series of patients with chronic stroke and traumatic brain injury and has *shown to improve performance during tasks of executive function*. A combination of meditation, body awareness, and yoga, MBSR is an active process thought to engage the frontal lobes. Based on our current understanding of pathophysiology, MBSR may serve as an attractive non-pharmacologic intervention to improve *subacute* post-stroke mood and cognitive dysfunction.

We will recruit a cohort of patients with minor stroke (NIHSS <8, modified Rankin score 0-2). Following baseline assessment of depression, fatigue, cognition, functional status, and patient satisfaction, individuals will be randomized to a standard 8 week MBSR course aimed at improving attention and concentration, and reducing anxiety and depression, or a bi-monthly standard Stroke Support Group (SSG). All patients will undergo reassessment post-intervention (~4-6 months post-infarct), along with MEG pre- and post-intervention. Participants will undergo neuroimaging pre- and post-intervention. We will evaluate differences in activation patterns and functional connectivity both at rest and during a visual cognitive task. We hypothesize that both groups will initially exhibit abnormal frontal lobe function compared to controls; however, after MBSR this will improve versus the SSG group.

Participants will also be administered a pre- and post-intervention Montreal Cognitive Assessment (MoCA), along with a battery of cognitive tasks to measure attention, concentration, processing speed, and executive function. Performance will be compared pre- and post-intervention, and for MBSR versus SSG participants. We hypothesize scores will be significantly better following MBSR compared to the SSG group. Finally, the PHQ9 and other measures of patient-reported outcomes (eg., mood) will be given to patients pre- and post-intervention and compared across groups at each time point. We hypothesize MBSR will improve rates of depression/anxiety compared to SSG. We will also evaluate patient satisfaction scores, measures of functional recovery: the modified Rankin scale (mRS) and Barthel Index (BI), and the likelihood of successful return to work. Individuals with minor stroke have tremendous potential to return to their baseline level of function, though often struggle. If effective in reducing post stroke mood and cognitive disorders for those with minor stroke, allowing them to return to work, MBSR will significantly reduce post-stroke morbidity and improve quality of life.

---

## 2. Objectives

Objective 1: To determine the effect of MBSR on abnormal cerebral activation patterns on MEG after stroke. Participants will undergo neuroimaging pre- and post-intervention. We will evaluate differences in activation patterns both at rest and during a visual cognitive task using cluster-based permutation tests. Patients in the MBSR and SSG groups will be compared to one another and to patients with no infarct

(previously collected cohort). T-tests and ANCOVA will be used to determine differences between groups at each time point. Functional connectivity studies will also be performed to evaluate differences between groups.

**Objective 2: To determine the impact of mindfulness training on post-stroke cognitive impairment.**

Participants will be administered a pre- and post-intervention Montreal Cognitive Assessment (MoCA), along with a battery of cognitive tasks to measure attention, concentration, processing speed, and executive function. Performance will be compared pre- and post-intervention, and for MBSR versus SSG participants.

**Objective 3: To determine the impact of mindfulness training on post-stroke depression.** The PHQ9 will be given to patients pre- and post-intervention and compared across groups at each time point.

*As secondary objectives we will also evaluate patient satisfaction scores, measures of functional recovery: the modified Rankin scale (mRS) and Barthel Index (BI), and the likelihood of successful return to work.*

### 3. Background

Stroke is common, affecting nearly 800,000 individuals in the United States each year. It is debilitating, the leading cause of long-term disability and 4th leading cause of death. It is costly, resulting in an average of \$36.5 billion dollars in healthcare expenditures and lost wages annually. Advances in treatment (intravenous tissue plasminogen activator and mechanical thrombectomy) have significantly reduced motor and language deficits, converting large hemispheric lesions into smaller infarcts with better overall long-term outcomes. Unfortunately, many patients arrive to the hospital too late to benefit from acute treatment, or continue to have symptoms despite intervention. Within our patient population, nearly 80% of individuals presenting for follow-up 4-6 weeks post-stroke report only “minor symptoms”, with low severity measured by NIH Stroke Scale (NIHSS) and modified Rankin scores (mRS). Though these individuals lack dense hemiparesis or aphasia; over half endorse some degree of cognitive impairment, mood disorder, or fatigue that significantly impacts recovery. These symptoms appear independent of stroke size, location, or depression.

Post-stroke dementia has an established basis in the literature and is common, particularly in those over the age of 60. However, rather than confusion or frank memory impairment, in the subacute phase of stroke recovery many patients endorse an alternative syndrome: difficulty with executive function, focus, concentration, and other aspects of attention. These deficits can be hard for others to appreciate, especially in previously high-functioning active individuals, but are detectable on screening tests such as the Montreal Cognitive Assessment (MoCA), and are debilitating. For example, such deficits may prevent an executive from effectively leading a business meeting, or a nurse from returning to the rapid pace of patient care. This may result in early retirement, particularly when the patient is older. The interpersonal difficulties caused by depression or low energy can result in divorce and social isolation. Preliminary data generated from our current American Heart Association (AHA)-funded study using magnetoencephalography (MEG), a tool measuring neurophysiologic processes in real time akin to EEG, suggest that individuals with stroke display delayed activation patterns of low amplitude with increased dispersion of activity during task completion compared to controls, and abnormal frontal lobe activity at rest. The significance of this activity is uncertain; however, it is noteworthy given the reported deficits of our patients involve predominantly frontal lobe functions. Some patients improve over time; however, the rate and degree of recovery are varied and difficult to predict. Often, before individuals recover, they have already made critical decisions that impact the rest of their life. Frustratingly, their disease is often under-recognized, and patients find little benefit from common strategies that target more severe impairment.

Mindfulness training may provide an attractive therapeutic option. The practice of mindfulness is quickly gaining popularity as an effective treatment for anxiety and depression, though the practice itself dates back to ancient traditions focused on healing and the power of the mind. Mindfulness Based Stress Reduction (MBSR) is an 8 week program comprised of meditation, body awareness, and yoga that is currently the most evidence-based of the mindfulness practices. Studies using MBSR to decrease anxiety and depression have predominantly been conducted in normal individuals and those with chronic disease states such as migraine, pain, vascular disease, and diabetes. In 2014, Abbott and colleagues conducted a meta analysis on all randomized controlled clinical trials of individuals with vascular disease (n=9) including one with chronic stroke patients and found improvement in stress reduction, depression, and anxiety after MBSR. The practice of mindfulness is an active process thought to exercise the frontal lobes leading to improved function. Studies on patients with Alzheimer’s disease have been promising, and in 2012, Johansson and colleagues showed that chronically after stroke or TBI, MBSR improved performance

on tests of executive function including the Symbol Digit Test and Trail Making Test. To date, mindfulness has not been evaluated in the subacute phase of stroke recovery, though this is a critical time when patients are making decisions that impact the rest of their lives. We believe that improving anxiety/depression and cognition during this time period would have significant impact on the success of an individual's reintegration into society, considerably improving post-stroke morbidity and reducing the burden of healthcare costs and lost wages.

#### 4. Study Procedures

- a. This is a prospective, randomized, controlled, longitudinal clinical trial that will make use of the following protocol:
  - Patients are admitted to the hospital for acute stroke and undergo work-up including MRI; they are entered into our Clinical Outcomes Database (routine clinical care, database is HIPAA compliant and has prior IRB approval). At this point, or at their first follow-up clinic visit, they will be identified and approached about participation in the study.
  - All patients are scheduled for an appointment in the Bayview Stroke Intervention Clinic (BaSIC) approximately 4-6 weeks +/- 4 weeks post-stroke
  - Seen at 4-6 weeks (routine care)- consented and tested if enrolled (per research protocol, as part of a prior approved study on Stroke Recovery)
  - Those meeting inclusion criteria for the Mindfulness and MEG study will be consented, randomized, and undergo the following additional procedures:
    - 1 month MEG visit at the University of Maryland (UMD, our current partner for our ongoing MEG study)- brain activity will be measured at rest and during cognitive tasks
    - EITHER 8 weeks of either MBSR Training and guided meditation using provided resources or participation in our bi-monthly Stroke Support Group
    - Repeat MEG following intervention (approximately 4-6 months post-stroke)
      - UMD MEG Protocol:
        - Magnetic fields will be recorded using a 275-channel whole-head MEG system (KIT System)

The MEG System non- invasively measures the magnetoencephalographic (MEG) signals produced by electrically active tissue of the brain. These signals are recorded by a computerized data acquisition system, displayed, and may then be interpreted by trained physicians to help localize these active areas. The location may then be correlated with anatomical information of the brain. MEG is routinely used to identify the locations of visual, auditory, somatosensory, and motor cortex in the brain. \* MEG is also used to non-invasively locate regions of epileptic activity within the brain. The localization information provided by MEG may be used, in conjunction with other diagnostic data, in neurosurgical planning.

#### *Indications used in this study*

The MEG System will non-invasively measure the MEG signals produced by electrically active tissue of the brain. These signals will be recorded by a computerized data acquisition system, displayed, and then be interpreted by trained *scientists* to help *characterize* and to localize these active areas *while the subjects are resting but awake, and while they perform several cognitive tasks*. The location will then be correlated with anatomical information of a *standard brain model or the subject's head MRI*. MEG will be used to identify the locations of visual, auditory, somatosensory, and motor cortex in the brain.

- The total length of the MEG recordings will depend on the length of the tasks (an estimate of 60 min has been used).
- Finally, patients will return for their 2nd post-stroke follow-up in BaSIC (routine care) and testing (if part of the Mindfulness or Recovery Study) following intervention (approximately 4-6 months post-stroke)
- b. We currently follow patients with minor stroke for 12 months post-infarct. They undergo additional testing as part of the study at their 1, 6, and 12 month follow-up visits. For this study, we will use MEG to map brain activity in individuals at the 1 and 6 month follow-up time points. This will require 2 visits to clinic at which time they will undergo testing, intervention with MBSR versus a Stroke Support Group, and 2 trips to the University of Maryland for MEG.
- c. The study is not formally blinded, as all patients who undergo imaging and intervention will have a stroke. However, the team at UMD will be initially blinded to stroke location, clinical symptoms, and

intervention. A control population for comparison already exists and for this pilot study we are interested in imaging affected individuals to determine differences.

- d. All participants will receive routine care. Intervention with MBSR/Support Group, and MEG testing will be performed above and beyond typical care and does not otherwise alter the treatment or monitoring course.
- e. There is a control group of patients of similar age without stroke who have already undergone MEG imaging and will be used as non-stroke control group; though the Stroke Support Group will allow for adjustment for socialization and activity as confounding factors (as the alternative intervention to MBSR)
- f. There is no concrete definition of treatment failure or removal criteria. We will use an intention-to-treat analysis; however also perform a per-protocol analysis. Attendance at 75% of MBSR or Support Group sessions will constitute full participation.
- g. There will be no change to the patient's care when the study ends. Participants may choose to leave the study at any time. Though they will not be fully compensated (see below) for an early drop-out, their data up to that point will be analyzed, and there will be no alteration in their care.

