## 7. Study Statistics

- a. Primary outcome variables include: MEG- changes in spectral properties and an estimate of the localization of spontaneous brain activity during resting state, functional connectivity during resting state. Clinical- performance on the MOCA and other cognitive measures (as part of the Recovery Study), patient-reported outcomes: fatigue, depression, satisfaction, quality of life.
- b. Secondary outcome variables include: changes in spectral properties, spontaneous brain activity, and functional connectivity during completion of various cognitive tasks.
- c. We will use an intention-to-treat analysis; however, we will adjust for degree of participation and consider an additional exploratory per-protocol analysis. For those lost-to-follow-up, data will be censored at the time they are lost. In addition to the proposed analyses, if there is evidence for an uneven distribution of confounding factors across treatment and control groups, we will perform multivariable linear regression to adjust for confounders (eg. degree of participation, age, sex, level of education, antidepressant use, and major medical co-morbidities (Charlson Comorbidity Index)).

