## 11. Costs

- MEG- cost for image acquisition as well as data processing and interpretation will be paid for through research funding by the PI (approximately \$500 per MEG).
- Travel costs- travel costs including travel to and from The University of Maryland will also be paid for by the PI using study funds. Patients may choose to arrive at the facility using a service such as Uber (trip paid for by the study team) or arrive to the facility themselves where they will be reimbursed for gas and parking.
- MBSR- the 8 week program will be provided at no cost to the patient as part of the study protocol.
- Stroke Support Group- SSG occurs bi-monthly and is run by the team at our Comprehensive Stroke Center. No additional funding is required.

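### The MEG team's blind to randomised arm has no stated end, and no masking is stated for cognitive testers or functional raters, so knowledge of arm could bias primary outcomes

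*Combined protocol and SAP*

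**What the plan says.** Section 4c states: "The study is not formally blinded, as all patients who undergo imaging and intervention will have a stroke". It then adds that "the team at UMD will be initially blinded to stroke location, clinical symptoms, and", and the sentence continues over a page break with the word intervention. The MEG team is therefore blinded to arm at the outset. No event or date ends the blind.

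Section 4 says that MEG signals will be "interpreted by trained *scientists* to help *characterize* and to localize these active areas". Section 7a lists as primary MEG outcomes "changes in spectral properties and an estimate of the localization of spontaneous brain activity during resting state, functional connectivity during resting state", and as primary clinical outcomes "performance on the MOCA and other cognitive measures (as part of the Recovery Study), patient-reported outcomes: fatigue, depression, satisfaction, quality of life". The MEG part of Section 7 adds between-group comparisons of regions of interest, peak amplitude and latency, without naming the regions or time windows.

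Section 2 gives as secondary objectives patient satisfaction and "measures of functional recovery: the modified Rankin scale (mRS) and Barthel Index (BI), and the likelihood of successful return to work". On post-intervention assessment, Section 4 says "patients will return for their 2nd post-stroke follow-up in BaSIC (routine care) and testing". No section says whether the people doing that testing know the arm.

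Section 8c describes regular, often real-time contact between the two sites and a monthly joint review of events. The pandemic addendum says that if MEG is suspended, cognitive outcomes alone will serve for the participants affected.

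**The concern.** The randomised contrast is MBSR versus SSG. That all participants have had a stroke explains why stroke status cannot be hidden. It is no reason to leave an assessor or analyst aware of which intervention a participant received, and the plan offers no other.

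Two sets of outcomes are exposed. The first is MEG, where the open choices (regions, windows, how peaks and latencies are extracted) could be made after a blind of undefined length has lapsed. The second is the examiner-administered tests and rated scales, for which no masking is stated. An examiner's or analyst's expectation can shift such measures, and the Abstract's hypotheses favour MBSR. Section 7 intends the treatment effect estimates to inform a larger trial, so a bias here would carry into that trial's planning.

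**Working it through.** **1. The plan's own figure.** The only relevant number is at least 20 per group (Section 7, MEG sample size). It cannot be reproduced, because no alpha, power, effect size or SD is given; it rests on experience with 9 stroke participants compared with controls. It is used below only as an input.

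**2. Masking to arm, outcome by outcome.**

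| Outcome | Status | Masking to arm stated |
|---|---|---|
| Resting-state MEG (spectral, localisation, connectivity) | Primary, 7a | Yes at first; end not defined |
| MEG during tasks | Secondary, 7b | Same |
| MoCA and cognitive battery | Primary, 7a | None stated |
| mRS, Barthel Index | Secondary objective, Section 2 | None stated |
| Fatigue, depression, satisfaction, quality of life | Primary, 7a | None stated; patient-reported, and masking participants is not realistic |

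**3. Is there a route by which arm could become known?** Section 4a lists randomisation before the first MEG visit, so an allocation exists at both recordings. Section 8c provides for frequent contact between the sites with no stated safeguard for the blind. Section 7c adjusts for degree of participation. MBSR is an 8-week course while SSG is described as bi-monthly, so raw attendance counts could reveal arm to an analyst.

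**4. What a bias of a given size would do.** Assumptions, none of them in the documents: two-sided alpha 0.05, outcome standardised to SD 1, no dropout, true effect zero, and knowledge of arm shifting the between-arm difference by b SD.

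- Standard error of the difference = √(2/20) = 0.316 SD
- Noncentrality = b / 0.316; degrees of freedom = 2 × 20 − 2 = 38; critical value t = 2.024
- False-positive rate = P(T > 2.024) + P(T < −2.024), with T noncentral t

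| Assumed shift b (SD) | Noncentrality | Upper tail | Lower tail | False-positive rate |
|---|---|---|---|---|
| 0 | 0 | 2.5% | 2.5% | 5.0% |
| 0.2 | 0.632 | 8.96% | 0.50% | 9.5% |
| 0.3 | 0.949 | 15.03% | 0.20% | 15.2% |
| 0.4 | 1.265 | 23.36% | 0.07% | 23.4% |

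**5. Does the small sample make this worse?** No. For the same shift of 0.2 SD, the rate is 7.1% with 10 per arm, 9.5% with 20, 16.8% with 50 and 29.1% with 100. A fixed shift inflates the error rate less in a small trial. It still passes in full into the effect estimate at any sample size, and the estimate is what the pilot is meant to supply.

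**The case against.** The strongest reply is that a safeguard exists and that the rest is silence rather than a bad choice. Four parts of it stand.

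- **UMD is blinded to arm at the start.** Because the sentence breaks across pages, a reader might infer that there is no MEG blind to intervention, or that MEG processing will be done with arm known. The text supports neither. The defect is the undefined duration.
- **Nothing says that testers know the arm.** A reader might infer that testers are wholly unmasked. The supportable statement is that no masking is stated here. The cognitive measures come from the separate Recovery Study, whose protocol is not part of these documents and may describe tester procedures.
- **The Costs section proves little.** It says that "SSG occurs bi-monthly and is run by the team at our Comprehensive Stroke Center". One might infer that the people leading SSG also test participants; the text does not say so. If they did, the direction of any bias would be unclear.
- **The numbers are illustrative.** The shifts are assumed. A two-sample t-test is not the cluster-based permutation test planned for MEG, and mRS and Barthel Index enter Section 7 as regression covariates rather than through a between-arm t-test.

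One might also assume manual artefact rejection or peak picking. The documents describe neither, and they do not say who chooses regions or runs the between-arm MEG analysis.

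What does not stand is reading *initially* as lasting until the analysis is complete, which adds a condition the protocol lacks. Pilot status is no full answer either: it weakens the false-positive framing, but biased estimates would still feed the next trial.

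**Conclusion.** The point holds in a limited form and should be acted on. The stated reason for not blinding does not concern the randomised arm. The MEG blind to arm exists but has no end point, while the MEG outcomes it should protect are primary and leave analytic choices open. No masking is stated for the examiners of the primary cognitive outcomes or for the mRS and Barthel raters, and cognitive results stand alone wherever MEG is suspended.

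The size of any bias is unknown. The false-positive rates of 9.5% to 23.4% depend on assumed shifts of 0.2 to 0.4 SD, a t-test and 20 per arm. They show sensitivity and do not predict what will happen. The conclusion rests on the wording of the plan, not on those figures. Masked assessment would protect the MEG, cognitive and mRS/Barthel outcomes; the patient-reported primary outcomes would remain open to expectation effects.

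**What to change.** **MEG (Section 4c).** Replace the initial blind with a blind to arm that lasts until pre-processing, region and time-window choices, peak and latency extraction, and the between-arm MEG analysis are locked. Specifically:

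- Use coded participant IDs and neutral group labels (A/B). Coded IDs alone do not give a masked between-arm comparison.
- Withhold or mask attendance data, until lock, for whoever processes and analyses the MEG data.
- Keep arm out of the routine contact between sites described in Section 8c.
- Drop the rationale about stroke status, or replace it with one about treatment arm. This clarifies the text but does not itself reduce bias.

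**Clinic testing.** Where existing staffing allows, have follow-up cognitive testing and mRS/Barthel rating done by staff who do not lead MBSR or SSG sessions and are not told the allocation. Ask participants not to disclose their group.

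**Reporting.** State that patient-reported outcomes, and any testing that cannot be masked, are unblinded, and interpret them accordingly.

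**Cost.** The MEG part needs protocol wording, coded labels and control of the attendance file, with no added staff; the downside is that UMD cannot see arm while troubleshooting. The testing part imposes a minor rota constraint. Because the documents do not describe staffing, it is conditional on people already in post.

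### The per-protocol comparison of 75% attenders lacks a consistent exploratory label and any baseline adjustment, so attendance that depends on mood, fatigue or cognition differently by arm can bias it in either direction

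*Combined protocol and SAP*

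**What the plan says.** Section 4, item f, says that intention-to-treat will be used, and adds in the same sentence and the next: "however also perform a per-protocol analysis. Attendance at 75% of MBSR or Support Group sessions will constitute full participation". It does not say outright that the per-protocol set is those who reach the bar, but that is the natural reading.

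Section 7, item c, again puts intention-to-treat first, but here the team will only "consider an additional exploratory per-protocol analysis". One section therefore commits to the analysis without a label, and the other treats it as optional and exploratory.

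Section 7 specifies t-tests and chi-square tests for cognition and for the PHQ-9, between arms at each time point and within arm over time. Item c adds multivariable regression only if confounders look unevenly distributed. Its examples begin "degree of participation, age, sex, level of education, antidepressant use" and go on to comorbidity. They do not name baseline PHQ-9, MoCA or fatigue. ANCOVA is mentioned for MEG, without named covariates.

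The two programmes are described in section 4, item a: "8 weeks of either MBSR Training and guided meditation using provided resources or participation in our bi-monthly Stroke Support Group". The abstract calls the first "a standard 8 week MBSR course". The support group is bi-monthly in the abstract, section 4a and section 11, but weekly in the pandemic changes at the end of the document. Exclusion criterion 6 also speaks of weekly sessions.

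**The concern.** Randomisation protects a comparison of everyone allocated. It does not protect a comparison of those who went on to attend. One set would be patients who kept up a course of meditation, body awareness and yoga; the other would be patients who kept up a support group. The abstract reports that more than 40% of this clinic population have significant cognitive, mood or fatigue problems, and section 7a lists cognition, depression and fatigue among the primary clinical outcomes. Section 8 plans to monitor for fatigue under MBSR. It is plausible that the same characteristics govern both attendance and outcome, and not to the same degree in each arm.

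At stake is how a per-protocol result would be read beside an inconclusive intention-to-treat result from about 20 patients per arm. Section 7 intends the effect estimates to inform a larger trial. An estimate from selected attenders could mislead that design, upwards or downwards.

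**Working it through.** **Inputs.** From the documents: at least 20 per group (section 7) and a bar of 75% of the participant's own group's sessions (section 4f). Not in the documents, and therefore assumed: 1:1 allocation, a two-sided 5% level, complete follow-up, attendance rates, and correlations of attendance with outcome. The plan has no figure of its own to reproduce here, because it gives no effect size, SD, power or attendance rate.

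**Bias with no treatment effect.** Let attendance be a latent normal variable with correlation r to a better outcome, cut so that a share p reaches the bar. The mean outcome among attenders, in SD units, is r × m(p), where m(p) = φ(z)/p and z = Φ⁻¹(1 − p). This gives m(0.60) = 0.644, m(0.70) = 0.497, m(0.80) = 0.350 and m(0.85) = 0.274. The per-protocol bias is r(MBSR) × m(p MBSR) − r(SSG) × m(p SSG); positive values favour MBSR. The rejection rates come from simulated no-effect trials with 20 per arm.

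| Reach bar, MBSR / SSG | r, MBSR / SSG | Bias (SD) | Two-sided rejections |
|---|---|---|---|
| 60% / 85% | 0.3 / 0.3 | 0.193 − 0.082 = 0.11 | about 6% |
| 60% / 85% | 0.5 / 0.2 | 0.322 − 0.055 = 0.27 | about 11% |
| 60% / 85% | 0.5 / 0 | 0.322 − 0 = 0.32 | 12–13% |
| 70% / 80% | 0.3 / 0.2 | 0.149 − 0.070 = 0.08 | 5–6% |
| 60% / 85% | 0.2 / 0.5 | 0.129 − 0.137 = −0.01 | about 5% |
| 60% / 85% | 0 / 0.3 | 0 − 0.082 = −0.08 | about 5% |
| 60% / 60% | 0.4 / 0.4 | 0 | about 5% |

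In the sixth row a false MBSR benefit becomes rarer than nominal (about 1.5% against 2.5%), so a real benefit would tend to be hidden. Intention-to-treat, comparing everyone as allocated, rejected in 4.8–5.4% of trials throughout.

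**A second model.** Here attendance was logistic in an underlying state of mood, fatigue and attention. Moderate differential selection gave biases of 0.17 to 0.36 SD. An extreme case (50% against 90% attending, selection in MBSR only) gave 0.43 to 0.52 SD. Selection in the support group only gave −0.18 to −0.22 SD, and equal selection gave about zero.

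**Effect of baseline adjustment.** Assume a baseline-to-follow-up correlation of 0.6 and attendance equally related to both. Adjustment then leaves roughly 1 − 0.6 = 0.4 of the bias: 0.27 × 0.4 = 0.11 and 0.32 × 0.4 = 0.13. Simulation gave 0.11–0.12 and 0.13–0.14. Rejections fell from 11–13% to about 6–7%, and the SD of the estimate from about 0.36 to 0.31. In the second model, false MBSR benefit in the scenarios selecting more strongly in MBSR fell from 6–26% to 4.1–8.9%, against a nominal 2.5%.

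**The bar itself.** Suppose each session is attended independently with probability 0.7 (assumed). Over 8 weeks:
- 6 of 8 (weekly): 28(0.7⁶)(0.3²) + 8(0.7⁷)(0.3) + 0.7⁸ = 0.55
- 3 of 4 (twice a month): 4(0.7³)(0.3) + 0.7⁴ = 0.65
- 1 of 1 (every two months): 0.70

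The readings of the support-group schedule alone move the share reaching the bar from 55% to 70%.

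**The case against.** The strongest reply is that the plan already gives this analysis little weight. Both sections put intention-to-treat first, section 7c calls the per-protocol analysis exploratory, and section 7 describes a pilot. That stands. A reader might infer that the trial's conclusion rests on the attenders, and the documents do not support that.

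A reader might also infer that the per-protocol analysis will manufacture an MBSR benefit. The documents do not support that either. They report no attendance, and the sign of the bias reverses when selection is stronger in the support group. Some features may narrow any gap: exclusion criterion 6 removes patients who cannot attend either programme, criterion 4 removes undertreated psychiatric illness, and section 10 pays $100 for reaching 75% and another $100 for full completion without distinguishing arms. None of these shows that attendance will be equal, but a large gap cannot be taken for granted. Nor is there a stated reason why attendance should track the MEG outcomes.

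The regression in section 7c is partial cover. Its covariate list is illustrative and not confined to intention-to-treat, but it is triggered only by apparent imbalance and names no baseline score.

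Finally, it is tempting to replace the per-protocol set with two-stage least squares, using allocation as the instrument for MBSR attendance. That requires allocation to act only through MBSR. Section 9 says support-group participants may benefit, and section 4e uses the group to account for socialisation and activity. If attending either programme were worth 0.3 SD (assumed), the instrumental estimate at the 60%/85% rates would be off by 0.3 × (0.60 − 0.85)/0.60 = −0.125 SD, as large as the bias in the first row of the table. Its SD is about 0.56 against √(2/20) = 0.32 for intention-to-treat.

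**Conclusion.** The concern holds in a limited form. The plan is inconsistent about the status of the per-protocol analysis, and it provides no routine adjustment of that analysis for the baseline scores most likely to drive attendance. The comparison can be biased in either direction: from about −0.1 to +0.3 SD towards MBSR in the 60%/85% scenarios, wider under more extreme assumptions, and zero if selection is equal. Even the larger biases in the table are below one standard error of the estimate (about 0.37 SD). All these figures rest on assumed attendance rates and correlations.

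Intention-to-treat is untouched by this selection, provided it compares everyone as allocated. The statement in section 7c that "we will adjust for degree of participation" is a separate matter: conditioning on participation could bring the same kind of bias into the main model, and it needs its own answer. This point is a low-cost improvement to a secondary analysis and does not undermine the main one.

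**What to change.** In sections 4f and 7c:

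- Define the per-protocol set explicitly and call the analysis exploratory in both places, with the same commitment to perform it or not.
- Adjust it for the baseline value of the outcome analysed, adding baseline PHQ-9 and fatigue where the sample allows. The abstract shows that depression, fatigue and cognition are assessed at baseline, so no new data are needed.
- Report attendance by arm and attenders' baseline scores by arm, beside the intention-to-treat result.
- State that adjustment reduces selection bias but does not remove it.
- Do not substitute two-stage least squares. At most, show it as an optional sensitivity analysis, stating the assumption that allocation acts only through MBSR attendance and why an active control makes that doubtful.
- Reconcile the support-group frequency across the abstract, sections 4a and 11, and the pandemic changes, and state the number of sessions on which 75% is calculated in each arm.

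The cost is a few sentences, a little analysis and a few degrees of freedom. With 12 and 17 attenders (60% and 85% of 20), an unadjusted comparison has 12 + 17 − 2 = 27; three covariates leave 24.
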